#### *8.1.6. Efficacy Analysis*

The primary assessment of efficacy in Phase II will be based on the ORR, which will be compared to 5% using a test of a single proportion. RECIST v.1.1 criteria will be used to determine the effect of AK-01 on tumor burden. ORR, duration of objective response, best response on study, progression-free survival, overall survival, and disease control rate may be summarized with descriptive statistics. The rate of disease control (stable disease, partial response, or complete response assessed by RECIST v. 1.1 in 2 consecutive scans) may be summarized by tumor type, as appropriate. Descriptive statistics will be used to analyze all tabulated efficacy data. Progression-free survival (PFS) and OS curves may be estimated using Kaplan-Meier methods.

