  - q. PK sampling will be performed in Cycle 1 of both Phase I and II at the following time points relative to the first dose on Day 1 and Day 15: 0 hours (pre-dose) and 1, 2, 4, 6, and 8-12 hours post-dose. Additional trough samples will be obtained prior to dosing on Day 2 and Day 8 of Cycle 1. The sampling schedule may be modified following review of PK data from the first cohort in Phase I to optimize collection times. A PK sample will also be obtained at the Discontinuation visit. A maximum of 3

additional PK samples may be drawn at other time points during the study, if warranted and agreed upon by both the investigator and the sponsor.

- r. A CT scan with IV contrast and assessment of tumor response by RECIST (v. 1.1, see Appendix 10) will occur within 1 week of the last dose of Cycle 2 and Cycle 4, and every 9 weeks ( $\pm$  1 week) thereafter for the duration of treatment. The schedule of tumor assessments will be maintained independent of any treatment schedule delays or changes. All CT scans will include the chest, abdomen and pelvis. For each tumor assessment, the date, method, and response evaluation will be recorded. Tumor response will not be evaluated at the screening CT scan (collected as the baseline). MRI may be performed instead of CT if a patient cannot tolerate CT contrast agents due to an iodine allergy. An individual patient will be monitored by the same methodology throughout the study. For patients that meet RECIST criteria for complete response or partial response, a confirmatory radiographic assessment will be obtained 4 weeks (+/- 5 days) after the response criteria was met.
- s. Dosing of AK-01 may continue until disease progression if the patient is receiving benefit and is experiencing no severe toxicity in the opinion of the investigator. Following Cycle 1, an entire cycle may be delayed or advanced by +/-1 day for administrative reasons, in which case it will be shortened (or lengthened) by 1 day, respectively.
- t. The discontinuation date will be recorded with the primary reason for discontinuation (if applicable). The patient will attend a Discontinuation visit as soon as possible after participation ceases.
- u. A CT scan and assessment of tumor response will be performed at the Discontinuation visit for patients who discontinue the study for reasons other than radiographic progression, and if a CT scan has not been performed within the prior 4 weeks.

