## 2. Changes from the Study Protocol

The exploratory study objective of Phase I (section 4.1 and 6.2) “To compare PD markers of AK-01 target engagement in tumor biopsies” stated in Study protocol version 4 was changed in type of biopsies to “To compare PD markers of AK-01 target engagement in skin biopsies”.

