#### Best Overall Response

Best overall response (BOR) is defined as the best response across all time point responses observed while on study treatment (for example, a patient who has stable disease (SD) at first assessment, partial response (PR) at second assessment, and progressive disease (PD) on last assessment has the BOR of PR). Only time point responses prior to PD or initiation of additional treatment (e.g. surgery, radiotherapy) will be included in the determination of BOR. When SD is believed to be best response, it must be observed at minimum 4 weeks since the Treatment start date to be considered for the BOR.

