#### Disease Control Rate

Disease control rate (DCR) is defined as a proportion of patients with BOR of SD, PR or complete response (CR) of those patients whose disease at baseline is assessable by RECIST v 1.1.1. Confirmation of CR and PR is required, as specified in RECIST v 1.1 guidelines [3], Table 3. The confirmatory scan in such cases must be performed at minimum 4 weeks-5 days, that is 23 days later.

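### The protocol counts disease control only when it is seen on two consecutive scans; the SAP counts a single stable-disease scan and does not declare the change

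*Protocol*

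**What the plan says.** **Protocol.** Section 8.1.6 says the rate of disease control may be summarised by tumor type, and defines control in a parenthesis as "stable disease, partial response, or complete response assessed by RECIST v. 1.1 in 2 consecutive scans".

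**SAP.** Section 6.1 takes as the DCR numerator every patient whose best overall response (BOR) is SD or better. It then adds: "Confirmation of CR and PR is required, as specified in RECIST v 1.1 guidelines". The confirming scan must come at least 23 days later. SD carries no such condition. The BOR paragraph reads "Best overall response (BOR) is defined as the best response across all time point responses observed while on study treatment", and for SD the only extra requirement is that "it must be observed at minimum 4 weeks since the Treatment start date to be considered for the BOR".

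**Scan schedule.** Protocol Appendix 1 (Phase II) says that CT "will occur within 1 week of the last dose of Cycle 2 and Cycle 4, and every 9 weeks" thereafter. It also says: "For patients that meet RECIST criteria for complete response or partial response, a confirmatory radiographic assessment will be obtained 4 weeks" after the criteria are met. SD triggers no additional scan.

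**Declared changes.** SAP Section 2 has one entry. It concerns "The exploratory study objective of Phase I" and changes the biopsy type. Neither that section nor the SAP's Table of Changes mentions DCR.

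**Role of DCR.** SAP 6.2 and 6.3 list it as exploratory in both phases. SAP 9.6.2 plans a summary with no hypothesis test.

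**The concern.** The two documents give one endpoint two meanings. Under the protocol a patient with SD must hold it on a second scan to count. Under the SAP the first scan is enough. The SAP states in its introduction that it follows protocol version 4, and its section for departures is silent on this one. A reader of the study report could therefore take the SAP's rate for the protocol's endpoint.

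What is at stake is how a supporting efficacy figure is read. One early SD scan is weaker evidence of control than two in a row, particularly in an uncontrolled study, so the looser rule gives the more favourable number.

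**Working it through.** **1. The definitions applied to the same patients (scans on schedule)**

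| Response pattern | Protocol 8.1.6 | SAP 6.1 |
|---|---|---|
| SD week 6, SD week 12 | controlled | controlled |
| SD week 6, progression week 12 | not controlled | controlled |
| SD week 6, no later scan | not controlled | controlled |
| PR week 6, confirmed about week 10 | controlled | controlled |
| PR week 6, progression at next scan | not controlled | unclear |
| Progression week 6 | not controlled | not controlled |

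The clear differences are in SD. The *unclear* row arises inside the SAP. The worked example in its BOR paragraph gives a BOR of partial response (PR) after one PR scan followed by progression, while its DCR paragraph requires confirmation.

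**2. Does the 4-week minimum stand in for the second scan?** Cycle 2 ends on day 2 × 21 = 42, which is week 6. A scan within 1 week of that falls at about weeks 5 to 7, beyond 4 weeks. For an on-schedule first scan the minimum therefore excludes nobody. It can exclude an early unscheduled or discontinuation scan.

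**3. Direction.** Let A be the patients with SD or better on two consecutive scans, B those with a qualifying BOR, and n the common denominator. Every patient in A has at least one qualifying scan and so is in B. Hence

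SAP DCR − protocol DCR = (number in B but not in A) / n ≥ 0.

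In a full Phase II cohort of 30, each patient in B but not in A adds 1/30 = 3.3 points. The argument assumes on-schedule scans and that an unconfirmed PR followed by SD still counts as at least SD. If the SAP dropped such a patient from DCR altogether, that patient would count under the protocol only.

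**4. Size.** Neither document gives a DCR value or target, or a median progression-free survival, so there is no planned figure to reproduce. The following is an illustration. Assume exponential time to progression with median m weeks, everyone scanned at weeks 6 and 12, SAP DCR = 0.5^(6/m) and protocol DCR = 0.5^(12/m).

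| Assumed m (weeks) | One scan | Two scans | Gap (points) | Patients in 30 |
|---|---|---|---|---|
| 6 | 50.0% | 25.0% | 25.0 | 7.5 |
| 8 | 59.5% | 35.4% | 24.1 | 7.2 |
| 12 | 70.7% | 50.0% | 20.7 | 6.2 |
| 16 | 77.1% | 59.5% | 17.7 | 5.3 |
| 24 | 84.1% | 70.7% | 13.4 | 4.0 |

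Moving the scans within 1-week windows (weeks 5 to 7 and 11 to 13) widens the range to about 9 points (m = 24, scans at weeks 7 and 11) to 34 points (m = 6, scans at weeks 5 and 13).

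**The case against.** **Low weight.** DCR is exploratory, optional in the protocol and descriptive in the SAP. The protocol's evidence criterion (Section 3.6) rests on response rate and durability, and the only efficacy test is on the response rate. This stands, and it limits the severity.

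**Nothing is hidden.** The SAP states its rule openly. Protocol 8.1.1 leaves the endpoints to the SAP and promises that deviations will be described in the study report. SAP 9.6.2 lists all tumor measurements and responses, so a two-scan rate can be recovered. This also stands. A reader might infer a mislabelled or irrecoverable result, and the documents do not support that. They do show that the section meant for departures omits this one, although it records a change to another exploratory item.

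**The illustration fits neither rule exactly.** A week-6 responder can have two consecutive scans by about week 10. A patient who stops without radiographic progression may have a discontinuation scan that serves as the second. DCR is analysed in the Efficacy Evaluable set, not in all treated patients. All of this is correct, so the gap in the table is not a prediction.

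**Other readings.** The two-scan phrase could grammatically attach to complete response alone, but it closes the whole parenthesis and that reading is strained. The protocol's RECIST appendix is redacted, so any rule on SD there cannot be checked.

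**Conclusion.** The definitions conflict and the change is undeclared. With on-schedule scans, a common denominator and an unconfirmed PR counted as at least SD where SD follows, the SAP's DCR is equal to or higher than the protocol's. It is strictly higher once any patient has one SD scan followed by progression or by no further scan. That direction needs no survival assumption.

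The size does. The 13 to 25 points depend on exponential progression-free survival, medians of 6 to 24 weeks and scans at weeks 6 and 12. None of the medians is in the documents. A reader might infer that DCR will be inflated by a known number of points, or that the SAP's DCR is simply a week-6 control rate. Neither follows: confirmed responders already need a second scan under the SAP, SD first seen at a later scan also counts, and the 4-week minimum can still exclude an early off-schedule scan. Nor is the primary response-rate analysis affected. This is a minor-to-moderate correction.

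**What to change.** Choose one definition before the SAP is executed.

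- **Preferred.** In SAP 6.1, count a patient as having disease control only if SD or better is seen on 2 consecutive scans, as in Protocol 8.1.6. Do not restrict this to scheduled scans. The protocol has no such limit, and adding one could exclude discontinuation or unscheduled scans and create a third definition.
- **Alternative.** Keep the single-scan SD rule, list it in SAP Section 2 with a reason, and report the two-scan rate beside it.

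In either case, state how an unconfirmed PR counts towards DCR, so that the BOR example and the confirmation requirement agree.

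The cost is a few lines of SAP text and one derivation from scans already collected. The reported DCR may be less favourable.

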#### *8.1.7. Molecular Profile Analysis*

Bioinformatics analyses may explore molecular profiles predictive of response or resistance to AK-01.

Measures of efficacy (as described in [Section 8.1.6](#)) for patients with different molecular profiles may be presented by patient, tumor type, and mutation, and in summary tables with descriptive statistics.

### **8.2. Missing Data**

In general, data imputation to accommodate missing data will not be performed. Patients who are not evaluable for PFS and OS will be considered censored at time zero. PFS will be censored at the time of last tumor assessment for patients lost to follow-up or who do not experience disease progression or death during the study. OS will be censored at the time of last contact for patients who are alive at study completion or who are lost to follow-up. For safety data, if the causality of an AE is unknown, it will be assumed there was a reasonable possibility the event was related to IMP.

### **8.3. Interim Data Analysis**

Safety and other available data will be evaluated prior to dose escalation in Phase I as detailed in [Section 3.1.3](#). In Phase II, once all patients within a cohort have completed at least 8 cycles of treatment, had disease progression, or discontinued IMP, data analyses for that cohort may be performed.

No formal interim data analysis is planned for this study.

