### 3.6. Determination of Sample Size

In Phase I, the 3 + 3 design dose escalates cohorts of up to 9 patients until the MTD is identified. Up to 6 additional patients may be dosed to inform the selection of a P2D. A sample size of approximately 30 patients was considered sufficient to identify the MTD and is not powered on the basis of statistical hypothesis testing.

In Phase II, up to 30 patients for each tumor type will be administered IMP (up to 120 patients total). An observed ORR (proportion of partial or complete responders by RECIST) of  $\geq 20\%$  with

a durability of at least 4 months will be considered evidence of efficacy. With 15 patients in a cohort, there is approximately 60% power to reject the null hypothesis of the ORR being  $\leq 5\%$  when the true ORR is 20% using a one-sided exact test for a single proportion at a significance level of 0.05. The power for this statistical test for a single tumor type without any adjustment for multiplicity is provided in [Table 2](#) using various observed ORRs.

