### 3.7. Study Completion

The study will be considered complete when all patients enrolled in Phase II have completed at least 8 cycles of treatment, experienced disease progression, or discontinued IMP (or unacceptable toxicity in the first cohort of Phase I prevents further dose escalation).

Once a given patient in Phase I or II has completed 8 cycles of treatment, AK-01 administration may continue until disease progression, so long as the patient is receiving benefit and is experiencing no severe toxicity in the opinion of the investigator. During this period, study assessments will be performed as described in Appendix 1. For patient discontinuation procedures, see [Section 4.2.1](#).

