### 5.2.2. Dose and Regimen

AK-01 will be administered twice daily, every day of a 21-day cycle. Patients will be dosed continuously: there will be no dosing holiday between cycles.

In Phase I, the dose of AK-01 will be between 25-75 mg BID per day (see [Table 3](#)). Patients in the first cohort of Phase I will receive 25 mg BID AK-01. Following a review of safety and other relevant data from this cohort, the SAC will decide on the dose for the subsequent cohort based on [Table 3](#). Following DLT or completion of Cycle 1, dosing for a given patient will be based on individual safety and tolerability.

For Phase II, the sponsor and SAC has established the dose of AK-01 as 25mg BID.

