## 9.12. Interim Analyses

Safety and other available data will be evaluated prior to dose escalation in Phase I as detailed in the Protocol. It is not part of this SAP.

In Phase II, once all patients within a cohort have completed at least 8 cycles of treatment, had disease progression, or discontinued AK-01, data analyses for that cohort may be performed. No formal interim data analysis is planned for this study.

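### The Phase II analysis may start at 8 cycles (week 24), which does not guarantee the follow-up needed to judge the protocol's 4-month durability criterion

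*Protocol*

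**What the plan says.** Four parts of the plan bear on this.

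- **Criterion.** Protocol 3.6 states that an observed ORR of at least 20% with "a durability of at least 4 months will be considered evidence of efficacy".
- **Trigger.** Protocol 8.3 sets the point for Phase II as "once all patients within a cohort have completed at least 8 cycles of treatment, had disease progression", or stopped study drug, after which "data analyses for that cohort may be performed". SAP 9.12 uses the same condition: "once all patients within a cohort have completed at least 8 cycles of treatment", with the same alternatives of progression or stopping drug. Protocol 3.7 applies it to the whole study: "The study will be considered complete when all patients enrolled in Phase II have completed at least 8 cycles of treatment", or have progressed or stopped drug.
- **Cycle length.** Protocol 5.2.2: "AK-01 will be administered twice daily, every day of a 21-day cycle".
- **Scans.** Appendix 1, footnote r, places tumor assessments "within 1 week of the last dose of Cycle 2 and Cycle 4, and every 9 weeks" after that, with a window of 1 week. The calendar does not move with dosing delays. A response is followed by a confirmatory scan 4 weeks later, plus or minus 5 days.

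Under SAP 6.1, duration of response starts at the first CR or PR, not at confirmation. Without an event it is censored at the last adequate tumor assessment. The SAP does not turn the 4-month criterion into an analysis rule.

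**The concern.** The trigger counts treatment cycles, while the criterion counts time from first response. That time can begin no earlier than the first post-baseline scan and can be shown only at later scans. At the earliest permitted analysis, the last patients enrolled may therefore have an ongoing response that has not been observed long enough to be called durable or not durable.

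What is at stake is the protocol's own statement of what would count as evidence of efficacy, together with the exploratory DOR summary. The cohorts are small, and 20% of 15, 20 or 30 patients is 3, 4 or 6 responders. One or two responders of unknown durability can leave that judgement open.

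**Working it through.** **The plan's own figure.** Protocol 3.6 gives no date for judging durability. Its only calculated design figure is power of about 60% for N=15. With H0 ORR ≤ 5% and one-sided 0.05, the exact test rejects at 3 or more responders: P(X≥3 | 0.05) = 0.0362 and P(X≥3 | 0.20) = 0.602. The figure reproduces. It contains no durability term, so it does not depend on what follows.

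**Trigger date.** 8 × 21 = 168 days = week 24.

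**Nominal scans.** The end of Cycle 2 is day 42 and the end of Cycle 4 is day 84. Then 84 + 63 = 147, 147 + 63 = 210 and 210 + 63 = 273, giving weeks 6, 12, 21, 30 and 39.

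**Four months in days.** The protocol does not define a month. 4 × 28 = 112, 4 × 30 = 120, and 4 × 30.44 ≈ 121.75.

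**Documented response for an ongoing patient at day 168 (last nominal scan day 147):**

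| First response | Documented at day 168 | First nominal scan showing 4 months |
|---|---|---|
| Week 6 (day 42) | 147 − 42 = 105 days | Week 30: 210 − 42 = 168 days |
| Week 12 (day 84) | 147 − 84 = 63 days | Week 30: 210 − 84 = 126 days |
| Week 21 (day 147) | 0 days; confirmatory scan not due until days 170 to 180 | Week 39: 273 − 147 = 126 days |

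The best case, 105 days, is below 4 months on all three definitions.

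**Scan windows.**
- With each scan tied to its nominal date, the longest span before week 24 is week 5 to week 22: 17 × 7 = 119 days. That is enough only with 28-day months.
- If each 9-week interval runs from the previous actual scan, an early first scan (week 5) and late later ones (week 13, then 13 + 10 = week 23) give 18 × 7 = 126 days, which qualifies.
- A PR at week 6 that first becomes a CR at week 21 gets a confirmatory scan at day 147 + 23 = 170 at the earliest, 128 days after first response. That is before week 30 but after week 24.

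**Size, under assumed accrual.** At the trigger, the last patient enrolled is at day 168, so anyone enrolled in the preceding 210 − 168 = 42 days has not reached week 30. Assume 30 patients, uniform accrual, a 20% ORR, and a last patient still on treatment at 8 cycles:
- 12-month accrual: 30 × 42/365 ≈ 3.45 patients; × 0.20 ≈ 0.7 responders.
- 6-month accrual: 30 × 42/182.5 ≈ 6.9 patients; × 0.20 ≈ 1.4 responders.

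For first responses at week 21 the gap is 273 − 168 = 105 days. If every response were that late, the figures would be 30 × 105/365 × 0.20 ≈ 1.7 and 30 × 105/182.5 × 0.20 ≈ 3.5. All these counts include responders who progress before the trigger, whose durations are already known.

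**The case against.** The strongest reply is that the rule permits an analysis and does not schedule one. It requires at least 8 cycles and says that analyses may be done. After 8 cycles, treatment can continue to progression with Appendix 1 assessments (Protocol 3.7), and end of trial comes later (Protocol 3.8). SAP 7.1 applies no cut-off date. SAP section 1 runs the analysis after database lock, which is not tied to 8 cycles. The week-30 and week-39 scans will therefore be taken and can count. This stands. A reader might infer that late-enrolled responders cannot meet the durability criterion, but that follows only if the sponsor locks at the earliest permitted moment. What remains is that nothing in either document prevents such a lock.

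A reader might also infer that 4 months can never be shown before week 30. That is true of nominal dates only, because the windows and the confirmatory-scan rule allow the exceptions worked out above. These need an unusual combination of early and late scans or a late change from PR to CR, so the plan should not rely on them.

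Finally, a reader might infer that censored responders would be counted as not durable, so that the error always goes against the drug. No rule says this. SAP 9.6.2 summarises DOR by Kaplan-Meier, which allows for incomplete follow-up. The documents are silent on how a responder censored before 4 months is classed against the Protocol 3.6 criterion, so no direction of error can be asserted.

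**Conclusion.** The mismatch is real but limited. If a cohort is analysed at the earliest permitted time, an ongoing responder among the last enrolled has at most 105 documented days on nominal dates, and neither document requires more response follow-up first. The shortfall is 6 weeks for first responses at week 6 or 12 and 15 weeks for a first response at week 21.

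The primary hypothesis test (Protocol 8.1.6, SAP 9.6.1) uses ORR alone and is not affected. The issue touches the evidence-of-efficacy statement in Protocol 3.6 and DOR, which SAP 6.3 lists as exploratory.

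The size rests on assumptions, because neither accrual nor lock date is given. Roughly 0.7 to 1.4 responders of 30 fall in the 42-day gap under uniform accrual over 12 to 6 months at a 20% ORR, and more if first responses are late. Against a benchmark of 6/30, that is enough to matter when the result is close.

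**What to change.** In Protocol 8.3 and SAP 9.12, and in Protocol 3.7 for consistency, keep the 8-cycle condition and add: the cohort efficacy analysis is run only once every responder has had a tumor assessment at least 4 months after first CR or PR, or has progressed, died or ended tumor assessments.

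The condition has to apply per responder. Requiring only the week-30 scan would not be enough within the allowed windows: a response first seen at week 13 and rescanned at week 29 has 16 × 7 = 112 days. The same edit should say how many days 4 months means, and how a responder whose assessments end before then is classed.

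The cost is wording in three places and a later analysis: about 6 weeks beyond the current earliest date, or about 15 weeks if a late-enrolled patient first responds at week 21. There is no wait if no late-enrolled patient has an ongoing response. No scans are needed beyond those already in Appendix 1, and no treatment rule changes.
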